3.7 Study Process

Sites participating in this study will be selected based upon their capabilities to successfully carry out those assessments. All patients considered for a RF ablation procedure for drug refractory recurrent symptomatic PAF should be screened by the investigator or designated member of the research team for study eligibility.

Pre-procedure assessments should be performed prior to the index AF ablation procedure. The AF ablation procedures for this study should follow 2012 CSPE fibrillation atrial treatment guidelines².

- Diagnostic catheter placement
- Electrophysiology study (under discretion of investigator)
- Transseptal puncture
- Cardioversion if subject is in AF (under discretion of investigator)
- Introduction of the Study Catheter
- CARTO® 3 mapping of the targeted Left Atrium (LA)
- Ablation of targets
- An isoproterenol intravenous challenge is required 0.5h after the CPVI procedure to confirm the entrance block and exit block

In the event of spontaneous or induced AF and/or atrial flutter, the placement of additional RF lesions outside of the PV ostia is at the discretion of the investigator. Any sheath except Agilis can be used in conjunction with ST catheter during the procedure. Cardioversion will be allowed if deemed clinically necessary by the investigator.

All subjects will be followed through one year after the index ablation procedure. Blanking period will span 90 days. After the index AF ablation procedure, subject follow-up visits are required at 3 months (Day 90; 76-104 days), 6 months (Day 180; 166-210 days), 9 months (Day 270; 240-300 days), and 12 months (Day 360; 330-420 days). Follow-up visit schedule will not reset if subject undergoes a repeat AF ablation procedure with the study catheter. At each visit, the following assessments should be performed: AF/AT/AFL recurrence and repeat ablation; ECG/24-hour Holter /TTM; Current AAD (including anticoagulation regime); Adverse events. The detail of the flow chart is shown in table 1.

Table 1: Data Collection flow chart

	Baseline/Pre-Ablation	Ablation	Discharge	3M [Days 76- 104]	6M [Days 166- 210]	9M [Days 240- 300]	12M [Days 330- 420]	Unexpected follow-up³
Visit	X			X	X	X	X	X
Informed Consent	X							
Demographics	X							
Medical history	X							
Ablation parameter values		X						
AF status	X		X	X	X	X	X	X
Previous and current cardiac medication	X		X	X	X	X	X	X
Current anticoagulation regime	X		X	X	X	X	X	X
ECG	X		X	X	X	X	X	X
24 h Holter	X			X	X	X	X	X
Examination to detect LA thrombi ¹	X							
TTM ²				X	X	X	X	X
AF/AT/AFL recurrence				X	X	X	X	X
Repeat ablation				X	X	X	X	X
Adverse events		X	X	X	X	X	X	X

1. To detect LA thrombi, e.g. routine TEE on the day or the day before AF ablation.
2. TTM transmission will be weekly during the first 8 weeks after the blanking period; After the first 8 weeks, asymptomatic transmissions will be transmitted monthly until the end of the 12-month follow-up visit. All symptomatic arrhythmia episodes should be recorded and transmitted at the time the event occurs.
3. If a subject returns for an arrhythmia related visit outside of the protocol-defined visit schedule provided, the visit will be considered “unscheduled” (UNS).

4 Study Endpoint

4.1 Primary Efficacy Endpoint

The primary effectiveness endpoint for this study is freedom from documented symptomatic

atrial fibrillation (AF), atrial tachycardia (AT), or atrial flutter (AFL) episodes through 12-month follow-up after the index ablation procedure (includes a three-month blanking period).

AF/AFL/AT qualifies as an arrhythmia recurrence after the first ablation if it lasts ≥ 30 seconds and is documented by ECG, HM or TTM, etc.

The following indicators will also be considered primary effectiveness failures and will be included in the effectiveness analysis population:

- Acute procedural failure (i.e., failure to confirm entrance block in all pulmonary veins with an isoproterenol intravenous challenge 0.5h post procedure or use of a non-study catheter to treat PAF)
- A repeat ablation beyond the 90-day blanking period

Atrial tachycardia/fibrillation atrial/auricular flutter recurrence events will be recorded and included in study analysis after a 90-day blanking period; recurrence during the blanking will not be considered treatment failure; re-ablation will not be recommended during the blanking^{1,2}.

4.2 Secondary Efficacy Endpoints

4.2.1 Acute Success Rate

Acute success is defined as confirmation of entrance block in all PVs with an isoproterenol intravenous challenge 0.5h post procedure.

The following test subjects will be considered as acute failures:

- Entrance block not confirmed for all PVs
- Subjects in whom a non-study catheter has been used for initial ablation of any AF targets

Acute failures will be considered primary effectiveness failures. Malfunction of a non-investigational catheter during the AF procedure will not be considered an acute failure.

4.2.2 CF and Force Time Integral (FTI) for index procedure by PV segments (from PV to the atrium, divided into 3, 6, 9 and 12 point position) (as shown in figure 1 below)

4.2.3 Number, percentage and sites of PV reconnection for the index procedure (from PV to the atrium, divided into 3, 6, 9 and 12 point position) (as shown in the figure below)

4.2.4 Total procedural time, ablation (RF) time and fluoroscopy time

4.3 Safety Endpoint

The incidence of AEs related with the procedure or study catheter

[figure not shown]

Figure 1: Right/left pulmonary veins was divided into 3, 6, 9 and 12 point position from PV to the atrium

5 Sample Size and Statistical Power

Assuming the true rate for freedom from documented symptomatic AF, AT, or AFL episodes through 12-months follow-up is about 65% using THERMOCOOL® SMARTTOUCHTM catheter with Contact Force Sensing Capability and a historic control performance goal of 50%, a sample size of 150 is needed in order to have 95% power to have the lower bound of the two-sided 95% confidence interval of this free-from-recurrence rate above the historic control performance goal¹. The calculation formula⁵⁴ was refer to the paper written by Xinran Tang.

nQuery Advisor® version 7.0 is used for calculation of this sample size. Assuming the dropout rate of the study is 20%, $150 / (1-0.2) = 188$ subjects is needed in total. About 200 subjects are planned to be enrolled in this study (at least 188 subjects).

6 Data Analysis

6.1 General Principle

All statistical procedures will be completed using SAS version 9.2 or later version. Statistical methods applied will be mostly descriptive statistics.

The continuous variables will be summarized by the statistics listed in table 2:

Table 2: Descriptive statistics of quantitative measures

Statistics	Decimal place preserved
N (Total number of patients in treatment group)	0

Confidential

n (Number of patients without missing values)	0
Mean, median, Q1, Q3	Preserve one more decimal place than the original data, up to no more than four decimal places
Standard deviation	Preserve two more decimal place than the original data, up to no more than four decimal places
Maximum, minimum	Preserve the same decimal place as the original data, up to no more than four decimal places

The categorical variables will be summarized with the frequency and percentage of each type. The missing value will not be included in the calculation of percentage, unless otherwise specified.

Kaplan-Meier method will be used for the time to onset of the first symptomatic AF, AT, or AFL episode. The statistics listed in Table 3 will be used to describe the results of statistical analysis model.

Table 3: Statistics of statistical analysis model

Statistics	Decimal place preserved
Q1, Q3, median	Preserve one more decimal place than the original data, up to no more than four decimal places
95% confidence interval	Preserve two more decimal place than the original data, up to no more than four decimal places
P-value	Usually preserve 3 decimal places (or <0.001, or >0.999)

Hypothesis testing will be carried out at the two-sided $\alpha=0.05$ level unless otherwise specified, and 2-sided 95% confidence intervals will be presented.

6.2 Analysis Population

6.2.1 Intent-to-treat (ITT) Population

Intent-to-treat (ITT) Population: All enrolled subjects who meet the inclusion/exclusion criteria and have signed informed consent form.

ITT Population will be used for baseline summary and provide analysis for primary efficacy endpoints.

6.2.2 Safety Analysis (SS) Population

Safety Analysis (SS) Population: All enrolled subjects who have undergone insertion of the study catheter during the procedure.

Safety Population will be used for the summaries for safety endpoints, secondary efficacy endpoints and other procedural data.

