Other potential complications, which may result from catheter insertion and manipulation as part of the prerequisite electrophysiology study and mapping procedure, include: Allergic reaction to the local anesthetic, sedatives, x-ray dye, heparin, protamine, or other agents administered during the procedure (risk <1%).⁴⁸⁻⁵² Arterial or venous injury, including arterial dissection, thrombosis, occlusion or hemorrhage at the catheter insertion sites or at other

sites along the vessels (risk <1%),^{35,36} which may produce hemorrhage, hematoma or ischemic injury to an extremity or major organ. Hemorrhage as a result of anticoagulation (risk <0.5%), which may require transfusion.^{35,36} Infection, either at the catheter insertion site or systemically, including endocarditis and septic emboli (risk <0.5%);³⁵⁻³⁷ this risk can be minimized by using standard aseptic technique and by the use of antibiotic agents when indicated.

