3.6 Subject Disposition

- **Enrolled Subjects:** patients who sign the informed consent.
- **Excluded Subjects:** subjects that are enrolled but never undergo insertion of the Study Catheter. Excluded subjects will not be evaluated in this study.
- **Discontinued Subjects:** subjects that have the investigational catheter inserted but are not treated with the investigational device (ie, no RF energy applied). Subjects will be categorized as "discontinued" if ablation was not possible due to non-investigational equipment failure or if their arrhythmia was determined at the time of electrophysiologic study to be a non-study arrhythmia (eg, atrial flutter).
- **Lost to Follow-up Subjects:** all subjects should be encouraged to return for protocol required office, clinic visit for evaluation during the study follow-up period. If a subject is unable to return for an office or clinic visit or unable to be contacted by telephone, 3 separate telephone calls should be made to obtain subject related safety information. All attempts should be documented in the source documents. If the subject does not respond to the 3 telephone calls, then the investigator must send a certified letter to the subject. If the subject does not respond to the letter, then the subject will be considered "lost to follow-up" for the current study visit. Subject contact must be attempted at each follow-up time point and if unable to contact the subject after 3 phone calls, the subject should once again be sent a certified letter. Only after failing to contact the subject at the final follow-up visit, the subject will be considered lost to follow-up and the study termination will be recorded in the individual case report form.
- **Withdrawn / Early Termination Subjects:** The investigator may remove a subject from the study for any of the following reasons: no longer meets eligibility criteria; withdrawal is in the subject's best interest; subject preference; concurrent illness; noncompliance; or any other situation the investigator deems a compromise to the integrity of the study. Subjects will be informed prior to study entry that they are free to withdraw from the study at any time and for any reason, without prejudice to his or her future medical care by the physician or the institution.

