4.2.4 Total procedural, ablation (RF) time and fluoroscopy time

4.2.5 The incidence of AEs related with the procedure and study catheter

[figure not shown]

Figure 1: Right/left pulmonary veins was divided into 3, 6, 9 and 12 point position from PV to the atrium

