5.4 General AF Procedure Guidelines

The AF ablation procedures for this study should follow standard clinical practice guidelines⁵³.

- Diagnostic catheter placement
- Electrophysiology study (discretion of investigator)
- Transseptal puncture
- Cardioversion if subject is in AF (discretion of investigator)
- Introduction of the Study Catheter
- CARTO® 3 mapping of the targeted Left Atrium (LA)
- Ablation of targets
- An isoproterenol intravenous challenge is required 0.5h after the CPVI procedure to confirm the entrance block and exit block

In the event of spontaneous or induced AF and/or atrial flutter, the placement of additional RF lesions outside of the PV ostia is at the discretion of the investigator and includes the following:

- Ablation at sites exhibiting complex fractionated atrial electrograms (CFAE)
- Linear lesions (if linear lesions are placed, it is recommended that complete conduction block across the ablation line be demonstrated)

- Ablation for any non-PV foci in the LA and/or RA

Any sheath except Agilis can be used in conjunction with ST catheter during the procedure. Cardioversion will be allowed if deemed clinically necessary by the investigator.

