8.3 Analysis Population

Intent-to-treat (ITT) Population: Enrolled subjects who meet the inclusion/exclusion criteria. ITT Population will be used for baseline summary and provide primary analysis for efficacy endpoints.

Safety (SS) Population: Enrolled subjects who have undergone insertion of the study catheter. Safety Population will be used for the summaries for safety endpoints.

Per-protocol (PP) Population: Subjects in the ITT Population who have undergone insertion of the study catheter and AF ablation procedure, and do not have other major protocol violations PP Population will be used to provide supportive analysis for efficacy endpoints.

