6.6 Safety analysis

Adverse events will be encoded to System Organ Class (SOC) and Preferred Term (PT) using the Medical Dictionary for Regulatory Activities MedDRA, version 18.0.

The analysis of adverse events will be based on treatment emergent adverse events (TEAE). An AE will be considered TEAE if (1) the AE has started on or after the date of the ablation procedure, or (2) the AE has started before the procedure but has worsened in severity on or after the date of the procedure.

All TEAEs, and TEAEs related with study device or ablation procedure, serious adverse events (SAEs), and SAEs related with study device or ablation procedure will be summarized and analyzed.

The number of subjects with TEAEs and the number of the events will be classified and described with System organ classification (SOC) and preferred term (PT), respectively.

Similar summary will be provided for the TEAEs related with study device or ablation procedure,

SAEs and SAEs related with study device or ablation procedure. At the same time, similar summary will be provided for TEAEs that occurred within 7 days of a study ablation procedure.

All the TEAEs, the serious adverse events leading to death, and all the serious adverse events are tabulated and analyzed in detail.

The number and percentage of subjects with TEAEs and SAEs will be summarized overall and by AE type, timing, seriousness, severity, causality, anticipated or not and outcome. Listing of AEs will also be provided.

7 Interim analysis

An interim analysis will be conducted in this study. The time of interim analysis is designated to be March 31, 2016, and the main aim is to provide summary descriptive statistics for baseline and procedure data. The results of interim analysis will not be used to change the sample size or discontinue the study.

The main content included in this interim analysis will be provided separately in another document.

8 Changes to planned analytical methods of the protocol

None.

9 Data processing principle

None.

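### The Safety Population starts at study catheter insertion, so a complication that ends the procedure before that step drops out of the procedure-related adverse event rate

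*SAP*

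**What the plan says.** The safety endpoint in Protocol 4.2.5 is "The incidence of AEs related with the procedure and study catheter". SAP 4.3 joins the two terms with an or, and SAP 6.6 likewise summarises events related to the device or the ablation procedure, so relation to either is enough. Protocol 6.6 defines procedure-related to include events tied to the standard electrophysiology procedure as well as to the ablation.

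The population for these summaries is narrower. Protocol 8.3 defines it as "Enrolled subjects who have undergone insertion of the study catheter" and SAP 6.2.2 as "All enrolled subjects who have undergone insertion of the study catheter during the procedure". SAP 6.2.2 adds: "Safety Population will be used for the summaries for safety endpoints, secondary efficacy endpoints and other procedural data".

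In Protocol 5.4, "Introduction of the Study Catheter" is the fifth of eight listed steps, and SAP 3.7 keeps the same order. Diagnostic catheter placement, an optional electrophysiology study, transseptal puncture and optional cardioversion come before it.

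Protocol 3.6 and SAP 3.6 class as Excluded those "subjects that are enrolled but never undergo insertion of the Study Catheter. Excluded subjects will not be evaluated in this study".

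SAP 6.6 counts an event as treatment-emergent if "the AE has started on or after the date of the ablation procedure", or if it began earlier and worsened from that date.

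**The concern.** The endpoint and the analysis set begin at different points. The endpoint starts with the procedure; the set starts part-way through it. In between lie steps that carry risk on the protocol's own account: Protocol 1.4.1 describes "Other potential complications, which may result from catheter insertion and manipulation as part of the prerequisite electrophysiology study and mapping procedure", and Protocol 6.2.3 names tamponade and vascular access complications among the anticipated events.

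If such a complication ends the procedure before the study catheter goes in, the complication itself removes the subject from the safety set. Membership then depends on the outcome being measured, and the lost events are those grave enough to stop the procedure. The study has no concurrent arm, so the absolute rate is the safety result and no comparison would show the shortfall.

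**Working it through.** **The plan's own figure.** The documents give no sample size, target or expected rate for safety. The only sample size is for effectiveness, and it reproduces. With n = 150, the smallest number of successes whose exact 95% lower bound exceeds 50% is 88, and the exact power at a true rate of 65% is 95.5% (stated: 95%). Then 150 / (1 − 0.20) = 187.5, rounded up to 188. None of this depends on the safety set. It supplies only N = 188 to 200.

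**Who is counted.** Setting the sections side by side:

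- Complication before insertion, study catheter inserted later: in the safety set, counted.
- Study catheter inserted, no energy applied (Discontinued): in the safety set.
- Complication before insertion that ends the procedure: procedure-related under Protocol 6.6, but outside the set in Protocol 8.3 and SAP 6.2.2, and not evaluated under section 3.6.

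Only the third group is lost.

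**Effect on the rate.** Let N subjects start the procedure. Let m be stopped before insertion by a complication, and let b others have a related event.

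- As written: b / (N − m)
- From procedure start: (b + m) / N
- Difference: m(N − m − b) / [N(N − m)], which is positive unless every inserted subject has an event

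The documents give neither m nor b. With N = 200 and b = 4 (an assumption), and exact 95% intervals in brackets:

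| m | As written | From procedure start | Difference (points) |
|---|---|---|---|
| 0 | 4/200 = 2.00% | 4/200 = 2.00% | 0 |
| 1 | 4/199 = 2.01% (0.55–5.07) | 5/200 = 2.50% (0.82–5.74) | 0.49 |
| 2 | 4/198 = 2.02% (0.55–5.09) | 6/200 = 3.00% (1.11–6.42) | 0.98 |
| 3 | 4/197 = 2.03% (0.56–5.12) | 7/200 = 3.50% (1.42–7.08) | 1.47 |

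The size hardly depends on b. At m = 1 and N = 200, b = 2 gives 197 / (200 × 199) = 0.49 points and b = 6 gives 193 / (200 × 199) = 0.48 points. At N = 188 with b = 4 it is 183 / (188 × 187) = 0.52 points.

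**How likely is m ≥ 1?** Protocol 1.4.1 puts cardiac perforation and vascular injury each below 1%, without dividing them into before and after insertion. Suppose the chance p of an abort due to a complication before insertion is 0.25% to 1% (an assumption). Then 200p = 0.5 to 2 subjects are expected, and the chance of at least one, 1 − (1 − p)^200, is 39% to 87%. If p is practically zero, nothing is lost.

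**Aborts without an event.** A procedure started and abandoned without any adverse event would enter the wider denominator only: 4/199 = 2.01% becomes 4/200 = 2.00%. It is therefore the event count that can only be understated; the rate could move the other way, but negligibly.

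**The case against.** The strongest reply is that little goes unseen. Protocol 6.1 and 6.7 require every adverse event to be recorded whatever its cause. Protocol 6.3 requires serious events to reach the sponsor within 24 hours and be notified to the ethics committee, with follow-up to resolution or stability. SAP 6.6 plans a listing and a detailed tabulation of serious events without naming a population, SAP 6.3.1 lists early terminations with reasons, and the mock tables are in a separate document. All of this stands: the loss is from the planned summaries, not from collection or reporting. It does not restore the event to the incidence, and no summary for Excluded subjects is specified.

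Second, a safety set defined by device exposure is a recognised choice, applied consistently in both documents. That suits an endpoint of catheter-related events. This endpoint also covers the procedure.

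Third, the mechanism and the numbers are partly assumed. No section says that an early complication stops the procedure. Vascular access is not a listed step in Protocol 5.4; it is implied by diagnostic catheter placement, whereas transseptal puncture is explicit. The perforation risk in Protocol 1.4.1 is attributed to catheter manipulation or energy delivery, not to transseptal puncture. The intervals above overlap heavily, and safety has no hypothesis or goal, so no pre-specified decision changes. This limits the size of the point but not its direction.

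A reader might go further and infer that Discontinued subjects can contribute no treatment-emergent event and have no follow-up, because SAP 6.6 and the visit schedule refer to the ablation. The documents do not support that. These subjects are in the safety set, SAP 6.6 uses a calendar date and elsewhere speaks simply of the procedure, and Protocol 5.5 follows all subjects for a year. At most, the reference date is ambiguous.

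**Conclusion.** The point holds as a mismatch between the endpoint and its analysis set. Read literally, the plan drops from its safety summaries any subject whose procedure is ended by a complication before study catheter insertion, so the number of procedure-related events can only be understated. The size is about 0.5 percentage points per such subject at N = 200, and zero if there are none. The documents do not say how many to expect; the 39% to 87% chance of at least one rests on the assumed abort probability.

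It would be wrong to infer that these events go uncollected or unreported, or that access and transseptal complications are lost in general: they count whenever the catheter is later inserted. The primary analysis, its sample size and its power are unaffected. This is a modest, inexpensive improvement that should be made.

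**What to change.** 1. **Protocol 8.3 and SAP 6.2.2.** For adverse event summaries, define the Safety Population as all enrolled subjects in whom the index procedure was started, taken as the first vascular puncture. Keep the catheter-inserted set as a second presentation. The secondary effectiveness and procedural summaries need not change.
2. **SAP 6.6.** Date treatment-emergent events from the start of the index procedure. This gives a reference date to subjects who never reach ablation and settles the ambiguity for Discontinued subjects.
3. **Protocol 3.6 and SAP 3.6.** Reconcile the statement that Excluded subjects are not evaluated with this safety set and with the ITT set. The ITT set (Protocol 8.3, SAP 6.2.1) has no insertion requirement, and SAP 6.5.1 counts subjects not followed to the endpoint as failures. Simply confining the statement to effectiveness would therefore be wrong, because it would take eligible never-inserted subjects, who are likely failures, out of the primary analysis.

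The cost is wording in these sections and the inclusion of a few aborted cases whose adverse events the protocol already requires to be recorded. The reported adverse event rate may be slightly less favourable.
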